The benefits of a HFib diet are supported extensively in the literature. Fiber protects against increasing body weight³⁰⁻³³, promotes fat loss³⁴⁻³⁹, increases satiety⁴⁰, and improves the metabolic and inflammatory profiles^{30,41-47}. Evidence that a HFib diet can reduce body weight and fat mass independent of a reduction in energy intake was highlighted in a recent meta-analysis⁴⁸ and a RCT in adults with MetS^{49,50}. The effect is hypothesized in part to be mediated through the powerful prebiotic effect of fiber that favorably shifts the gut microbiota leading to reduced weight gain⁴⁸, inflammation⁵¹, improved metabolic profile⁵¹, and prevention of fat accrual^{34-37,51}. Our working hypothesis is that consuming a HFib diet (≥ 30 g/day) will reduce GWG and fat accretion by diluting energy density, reducing hunger thereby reducing energy intake, and changing the gut bacteria composition. Our pilot data (n=20) found a 12 wk HFib pregnancy intervention reduced Firmicutes and increased Bacteroidetes, which was associated with reduced weight gain and fat accretion⁵². Current fiber intake of pregnant women is 17.3 g/day⁵³, well below the recommended intake (28 g/day⁵⁴), and triggering fiber to be classified as a nutrient of concern⁵⁵. Thus, increasing fiber intake has high potential for impact. However, RCTs in pregnant women are lacking to understand if this is an effective intervention strategy.

The project objective is to block randomize n=56 pregnant women to either a HFib diet or usual care. Eighteen weekly lessons will educate women on eating a HFib diet. To ensure fiber intake is met, daily snacks (10-12 g/day) will be provided. Weight gain, fat accretion, and stool microbiota will be measured twice during pregnancy (pre- and post-intervention) and assessed at 2 months, 6 months, and 12 months postpartum. Infant body composition will be measured at 2 weeks, 2 months, 6 months, and 12 months. The aims are:

Primary Aim 1: Assess the between group difference in maternal weight gain and fat accretion. H1: The HFib group will gain less weight and accrue less fat mass when compared to the control group.

Primary Aim 2: Compare fiber intake and dietary quality between groups. H2: The HFib group will consume more fiber and have a higher diet quality during pregnancy and postpartum.

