Secondary Aim 1: Characterize between group differences in the gut microbiome composition and diversity (alpha and beta). H1: The HFib group will have a greater change in gut microbiota composition, taxonomy, and diversity that will be detected during pregnancy and postpartum.

Secondary Aim 2: Determine if there are between group differences in early infant fat accrual. H2: Offspring born to women in the HFib group will have lower fat accrual.

Secondary Aim 3: Determine if there are differences in markers of metabolic, inflammatory, and brain health during pregnancy and postpartum. H3: The HFib group will be characterized by more favorable levels of metabolic, inflammatory, and brain health markers at all time points measured.

Impact: Prior intervention design has not addressed the MetS state of normal pregnancy. Dietary fiber counteracts the components of the MetS. Increasing fiber intake may positively impact the drivers of poor maternal outcomes that prior studies failed to show. Our study has potential to succeed where others have failed because we designed treatment to target the metabolic shifts that occur during normal pregnancy. This proposal is innovative because we are measuring the intervention impact on fat accrual and the microbiota in mother and early offspring fat accrual. This proposal would fill a large research gap.

RESEARCH STRATEGY

A) SIGNIFICANCE

A1) Why maternal excessive weight gain is an important problem: Overall, 55% of women gain excessive gestational weight^{3,4} though disparities exist within BMI groups; 62% of women with a high normal BMI (22-24.9 kg/m²) and ~70% of overweight and obese women gain excessively^{3,4}. Maternal overweight and excessive gestational weight gain (GWG) are associated with poor offspring outcomes including increased infant fat mass (FM)^{3,56} and increased FM in childhood^{57,58} and adulthood⁵⁹. Research shows a strong relationship between maternal excessive GWG and offspring obesity development^{60,61}, diabetes, and cardiovascular disease^{62,63}. Maternal conditions related to excessive GWG include hypertension^{64,65} and gestational diabetes (GDM)^{66,67}. Many women develop overweight or obesity during the childbearing years⁶⁸. Women who gain excessively are more likely to retain 10 to 20 lbs at 12 months postpartum⁶⁹. Effective interventions to prevent excessive GWG are desperately needed.

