C2) Population to be studied: Women between 9 to 19 weeks pregnant with a BMI 18.5 – 45.0 kg/m² and between the ages of 18-45 years will be recruited from the University of Kansas Medical Center (KUMC) OB clinics. We will enroll all race/ethnic groups. Participant's routine OB care will be managed by their primary Obstetrician. Any interventions, laboratory or other evaluations, and decisions regarding delivery will be made by the primary Obstetrician. Groups of 6-10 subjects will be block randomized to control or the intervention group to ensure adequate size for optimal group dynamics. The intervention will start at 12-20 wks and last 18 weeks, ensuring intervention completion by 38 weeks in pregnancy. We will screen women to determine the current dietary fiber intake. If they are consuming 25 g/day of fiber or more, they will be excluded from the study. Women who do not have internet and phone access will be excluded from the study. Participants must be willing to consume provided snacks. Participants will also be excluded if they have history of gestational diabetes (GDM), diabetes, pre-eclampsia, hypertension, heart disease, hypothyroidism, or other metabolic abnormalities, current hyperemesis gravidarum, eating disorder, smoking, or are pregnant with multiples. Women that develop any of these medical conditions during pregnancy will be accounted for in the final analysis. Deviations from inclusion criteria will be at the discretion of the PI.

C3) Recruitment: We have access to the electronic clinic schedule, therefore we have the exact date and time of the recruit's OB visit. We have worked directly with physicians and staff providing an in service at meetings to ensure a smooth recruiting process so that we do not impede clinic flow. Annually, 1800 women are managed in the OB clinics at KUMC. Additionally, we will recruit using an electronic flyer via social media. Individuals who have agreed to future contact from previous studies will also be approached if eligible via email or phone.

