C7k) Maternal blood draw: Maternal venous blood will be collected at 5 times through the study (baseline, end of intervention, 2 months, 6 months, and 12 months postpartum) after an overnight fast by a trained phlebotomist. A total of two 4-mL EDTA (lavender top) tubes (1 will be filled ½ full), one 10-mL EDTA, one 7.5-mL serum (tiger top) tube, and one 8.5mL serum tubes will be collected. At the baseline visit and additional one 6-mL ACD (yellow top) plasma vacutainer will be collected for ApoE genotyping. All tubes will be placed on ice and processed within 24 hours, including aliquoting for analysis. All tubes will be appropriately labeled with the study identification number, date (mm/dd/yyyy), and time (24-hour time, hh:mm). Blood samples will be analyzed to assess biomarkers related to cardiometabolic health (including serum lipids, glucose metabolism, and inflammation), gut metabolites (short chain fatty acids) and neuronal health (including assessment of underlying ApoE genetics). Samples will be sent to Quest Diagnostics for cardiometabolic markers (standard lipid panel (total cholesterol, triglycerides, HDL-C, LDL-C (calculated), Cholesterol/HDL ratio (calculated), and non-HDL-C (calculated)), hemoglobin A1C, plasma glucose, serum insulin, and high sensitivity- C-reactive protein). All other samples will be stored at -80°C for analysis. Batched samples will be analyzed at KUMC according to the protocols of the manufacturer using the following formats:, SIMOA (neurofilament-light and inflammatory cytokines), and polymerase chain reaction (ApoE genotype). Unused samples will be banked for future evaluations related to nutrition and brain health including free cell RNA analysis at KUMC.

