C7t) Breastmilk analysis: Participants who choose to breast feed will be asked to pump one breast until empty, homogenize the breastmilk by stirring, and return 20-mL to the study team for nutrient analysis. Participants will be asked to do this at 1 month, 2 months, 3 months, 4 months, 5 months, and 6 months, freeze it, and return it to the study team at the 2-month and 6-month visits. The remainder of the breastmilk collected can be kept by the participant and fed to their infant. Any leftover sample after initial nutrient analysis will be banked for future evaluations related to nutrition and brain health and KUMC.

C8) Steps to maximize adherence and retention: We will be using incentives for study visits, incentives for reporting goals, and regular short-term performance and feedback.

C8a) Incentive system: Participants will be compensated \$100 for each of the 6 study visits: baseline, end intervention, 2 weeks postpartum, 2 months postpartum, 6 months postpartum, and 12 months postpartum totaling up to \$600 for completion of all visits. Participants asked to return for repeat infant DXA (no more than 2 at each study timepoint) will be compensated an additional \$50. Compensation will be provided on a ClinCard, which is given at enrollment. After each visit study staff will load their unique card number with the respective pay. Participants can use the card anywhere Mastercard is accepted, and study staff does not have access to where the money will be spent.

C8c) Monitoring retention: When participants miss a session or reporting of behaviors, they will be contacted and a standardized protocol according to attendance and adherence demands will be used to make every effort to retain the participant or encourage reporting. This will be documented and used for program evaluation.

C9) Statistical analysis: The purpose of this study is to attain feasibility data therefore the small sample size does not afford the power to detect significance but to identify promising trends and relationships.

Analysis for Aim 1 H1: A t-test will be used to determine if there is a difference in maternal weight gain and fat accretion between the two groups.

Analysis for Aim 2 H2: A t-test will be used to quantify if there is a difference in fiber intake and dietary quality between the two groups.

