Analysis for secondary Aim 1 H1: Repeated measures ANCOVA will be used to assess the difference in gut microbiome composition and diversity from baseline to study end between groups.

Analysis for secondary Aim 2 H2: A t-test will be used to determine if there is a difference in infant fat accrual between groups.

Analysis for secondary Aim 3 H3: A t-test will be used to determine if there is a difference in metabolic, inflammatory, and brain health markers.

Process evaluation: A process evaluation will be completed.

C10) Study challenges: A primary study challenge is the recruitment and retention. [name] has completed protocols successfully recruiting participants from the OB clinics at KUMC. [name], KUMC head of OBGYN, reports 1800 annual deliveries take place at KUMC with ~40% overweight. A second challenge is to assure the fidelity of the interventions. [name] will listen to 20% of GBPC sessions and compare the content delivered to a standardized checklist. If less than 80% of content is covered, [name] will re-train the Dietitian. A third challenge is to ensure subjects are attending sessions and reporting behaviors. We had a high degree of weekly reporting in our pilot study and anticipate a similar response rate in this pilot.

C11) Expected results: We anticipate the Hfib intervention will successfully prevent excessive GWG. The Hfib intervention holds promise to be delivered in routine clinical care. If the results are positive, the next study would be to adapt and embed the Hfib intervention in routine clinical care. The literature supports preventing excessive GWG has a high likelihood to greatly improve the health of both mothers and their offspring however there is variable success in published interventions. This supports the need to design and test interventions informed by prior study failures.

C12) Environment: The environment at KUMC is well suited to conduct this research.

References:

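### Secondary Aim 3 names a t-test with no baseline covariate and no stated scale or visit, although the blood markers are measured at baseline and at four later visits

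*Combined protocol and SAP*

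**What the plan says.** Section C9 (Statistical analysis) gives secondary Aim 3 one sentence: "A t-test will be used to determine if there is a difference in metabolic, inflammatory, and brain health markers". It does not say whether values are compared on the raw or log scale, at which visit, or as follow-up levels or changes from baseline. No covariate is named.

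The hypothesis under Specific Aims is broader. The high-fiber group is expected to show "more favorable levels of metabolic, inflammatory, and brain health markers at all time points measured".

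Section C7k sets the sampling: "Maternal venous blood will be collected at 5 times through the study (baseline, end of intervention, 2 months, 6 months, and 12 months postpartum". The panel is mixed. The clinical laboratory reports a lipid panel together with "hemoglobin A1C, plasma glucose, serum insulin, and high sensitivity- C-reactive protein", and batched assays cover "SIMOA (neurofilament-light and inflammatory cytokines".

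On size, the plan is to "block randomize n=56 pregnant women to either a HFib diet or usual care". C9 adds that "the small sample size does not afford the power to detect significance but to identify promising trends and relationships". For the microbiome aim, C9 names a repeated measures ANCOVA.

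**The concern.** Each woman's own marker level before the intervention usually predicts her later level. The Protection of Human Subjects section places baseline testing before the intervention starts, so the baseline value is a legitimate covariate. A two-group t-test on follow-up values leaves all between-woman variation in the error term. With about 28 women per arm, it also carries any chance baseline imbalance straight into the estimated difference.

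The hypothesis concerns several visits, but the method names none. Scale and visit could therefore be chosen after the data are seen. For markers with a long right tail, a few high values could dominate a raw-scale mean difference.

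At stake is the precision of the estimates that this feasibility study would pass on to the design of a later trial.

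**Working it through.** **Stated figure.** There is none to reproduce. The protocol gives 56 women without an alpha level, power, effect size or SD, and it disclaims power.

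**Inputs from the protocol.** Total 56 women; one baseline and four later blood draws; a t-test for the markers.

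**Assumed inputs.**
- 1:1 allocation, so 56/2 = 28 per arm. C2 says only "Groups of 6-10 subjects will be block randomized to control or the intervention group".
- Two-sided 5% test.
- Correlation ρ between baseline and follow-up of 0.3 to 0.7.
- SD of log values of 0.1 to 1.2.
- True effect of 0.6 SD on the log scale.

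**Step 1: baseline adjustment, in closed form.** Using baseline as a covariate multiplies the residual SD, and so the interval width, by √(1 − ρ²). The equivalent sample size is 28/(1 − ρ²) per arm. The effect detectable with 80% power (normal approximation) is (1.96 + 0.84) × √(2/28) × √(1 − ρ²) = 0.749 × √(1 − ρ²) SD.

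| ρ | √(1 − ρ²) | Interval narrower by | Equivalent n per arm | Detectable effect (SD) |
|---|---|---|---|---|
| unadjusted | 1.000 | – | 28 | 0.75 |
| 0.3 | 0.954 | 5% | 31 | 0.71 |
| 0.5 | 0.866 | 13% | 37 | 0.65 |
| 0.7 | 0.714 | 29% | 55 | 0.53 |

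This step applies on whichever scale the marker is roughly normal, so it does not rely on skewness.

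**Step 2: scale and adjustment together, by simulation.** Baseline and one follow-up value were drawn as bivariate log-normal, 28 per arm, 20,000 trials per setting. Power at an effect of 0.6 log-SD and ρ = 0.5:

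| Log-SD | Implied ratio of geometric means | Raw t-test | Log t-test | Log ANCOVA |
|---|---|---|---|---|
| 0.1 | 0.94 | 59% | 60% | 71% |
| 0.3 | 0.84 | 58% | 60% | 71% |
| 0.5 | 0.74 | 55% | 60% | 72% |
| 0.8 | 0.62 | 49% | 60% | 72% |
| 1.0 | 0.55 | 43% | 59% | 71% |
| 1.2 | 0.49 | 37% | 60% | 71% |

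Log ANCOVA reaches about 63% at ρ = 0.3 and 86–87% at ρ = 0.7. The gain splits as follows:
- Log transformation alone: 0–1 point at log-SD 0.1, about 2 at 0.3, 5 at 0.5, 12 at 0.8, 17 at 1.0 and 23 at 1.2.
- Baseline adjustment on the log scale: about 3–4 points at ρ = 0.3, 11–12 at 0.5 and 27 at 0.7.
- Both together, against a raw t-test: from 4 points (log-SD 0.1, ρ = 0.3) to 50 points (log-SD 1.2, ρ = 0.7).

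**Step 3: sensitivity to effect size.** For a fixed 30% reduction at ρ = 0.5 and 28 per arm, raw t-test against log ANCOVA gives 70% vs 85% at log-SD 0.5, 30% vs 47% at 0.8 and 18% vs 32% at 1.0. With 25 per arm and log-SD 0.8:
- Ratio 0.6, ρ = 0.6: 49% vs 78%, a gain of 29 points.
- Ratio 0.6, ρ = 0.3: 48% vs 62%, a gain of 14 points.
- Ratio 0.8, ρ = 0.3: 13% vs 17%, a gain of 4 points.

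**Step 4: a t-test on change from baseline.** The wording would also allow this. Its variance is proportional to 2(1 − ρ), against 1 for follow-up alone and 1 − ρ² for ANCOVA. It is worse than ignoring baseline when ρ is below 0.5, and never better than ANCOVA apart from the one degree of freedom that ANCOVA spends. On the raw scale at log-SD 0.8, change-score power is 27%, 35% and 50% for ρ = 0.3, 0.5 and 0.7, against about 48% for the plain follow-up comparison.

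**Step 5: type I error.** With no true effect, the raw t-test rejected in 3.5% to 4.6% of trials at log-SD 0.5 to 1.2. It is not inflated.

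**The case against.** Several points on the other side have force.

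- **Scale.** A reader might infer that the plan commits to the raw scale and to a separate test at each visit. It says neither. A t-test on log values, or on change from baseline, would comply. What stands is that no form of the named test carries baseline as a covariate, and that scale and visit are left open.
- **Skewness.** A reader might infer that the whole panel is skewed. The documents give no distribution for any marker, and the panel includes HbA1c, glucose and cholesterol, where a log transformation may change little. Expecting right skew in hs-CRP, insulin, triglycerides, cytokines and neurofilament-light is general knowledge about such markers, not something the protocol states. Baseline adjustment can help whether or not a marker is skewed.
- **Power.** A reader might infer that much of the available power is thrown away. C9 claims no power, the aim is secondary, and the gain can be as small as 4 points. For modest effects, every method has low power at this sample size. The argument is therefore about precision. A study meant to identify trends still benefits from tighter estimates.
- **Correlation.** Baseline falls in pregnancy and the last visit is 12 months postpartum, so correlation may be weak at late visits. That is why ρ = 0.3 is in the range.
- **Model simulated.** The simulation covers one visit, not a four-visit mixed model. With complete data, visit-specific group effects and visit-specific baseline slopes, an unstructured mixed model gives the same visit estimates as separate ANCOVAs. Its behaviour with missing visits was not examined.

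**Conclusion.** The point holds as one of efficiency and pre-specification. The named test makes no use of baseline as a covariate, although the sample is scheduled and C9 already adopts a repeated measures ANCOVA for another aim. The cost is precision: intervals wider than they need be, by an amount that depends on the baseline correlation. Adjustment shortens them by roughly 5% to 29% over correlations of 0.3 to 0.7. The 4-to-50-point range in single-visit power rests wholly on the assumed allocation, effect, log-SDs and correlations, and its upper end needs both strong skew and high correlation.

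The documents do not support reading this as a validity failure, as a raw-scale commitment, or as a broken power claim. It is an inexpensive improvement to a secondary aim of a feasibility study.

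**What to change.** In C9, replace the Aim 3 t-test for all blood markers with a baseline-adjusted analysis: an ANCOVA at each visit, or one mixed model over the four post-baseline visits with group, visit, group-by-visit, baseline and baseline-by-visit terms. Treat baseline as a covariate and not as a tested time point. Report the group difference at each visit with a 95% confidence interval, to match the hypothesis about all time points.

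List in advance the markers to be log-transformed because right skew is expected (for example hs-CRP, insulin, triglycerides, cytokines and neurofilament-light). Use log baseline as the covariate for these and report ratios of geometric means. Keep the remaining markers on their measured scale, also baseline-adjusted.

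The cost is a few lines of analysis text, with no added visits, samples or participants. The downside is that log-scale results are read as ratios rather than differences in measured units.

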This study will enroll pregnant women and their offspring. This study will block randomize 6-10 women into one of the following groups: a high fiber dietary intervention or UC. The primary aim is to assess the difference in maternal weight gain and fat accrual. All subjects will be given a body weight scale and report weekly their body weight. This allows close supervision of progression of each participant to ensure the intervention is not overly effective and all women are gaining adequate body weight. If a woman gains or loses more than 5 pounds over a two-week period, she will be contacted and her diet habits and fiber intake will be reviewed. Additionally, she will be asked if she is willing to provide her Obstetrician contact information and would like us to contact her Obstetrician. If so, a report will be sent to her Obstetrician. Infant growth will be charted and marked for review if crossing of two or more major percentile lines occurs. During pregnancy, maternal diet and body composition will be measured. A maternal DXA scan will be obtained at 2 weeks, 2 months, 6 months, and 12 months postpartum. Infant birth characteristics will be extracted from the electronic medical record. Infant body weight and body composition will be measured at 2 weeks, 2 months, 6 months, and 12 months using the Pea Pod. An infant DXA scan will be obtained at 2 weeks, 6 months, and 12 months.

RISKS TO HUMAN SUBJECTS

Human Subjects Involvement, Characteristics, and Design

- (1) *Patient recruitment and informed consent.* All recruitment, consent, and data forms for the study proposal will be approved prior to any enrollment. Informed consent for continued testing is obtained by a trained research team member with NIH-approved Human Subjects' protection certification. Consent includes the standard elements: a study description, the potential risks, benefits and options for nonparticipation. All subjects are informed they are free to withdraw from the study without changes in their usual care. Consent is documented as a signed form and will be kept in a locked file at the study office. The study is conducted in accordance with ethical principles founded in the Declaration of Helsinki. The IRB review includes a review of all appropriate study documentation to safeguard the rights, safety and well-being of the subjects. The protocol, informed consent, written information given to the subjects, safety updates, annual progress reports, and any revisions to these documents are provided to the IRB by the principal investigators. The method of obtaining and documenting the informed consent and the contents of the consent will occur either in person or online and comply with GCP and all applicable regulatory requirement(s).
- (2) *Describe the characteristics of the subject populations and identify criteria for inclusion and exclusion.* Subjects will consist of pregnant women and their infants. Pregnant women will be consented for their participation and the participation of their infant in the study. Women will be between the ages 18-45 years old; all racial/ethnic groups will be recruited between 9-19 weeks pregnant; can be first or greater pregnancy; BMI range: 18.5-45 kg/m². If they are consuming 25 g/day of fiber or more, they will be excluded from the study. Women who do not have internet and phone access will be excluded from the study. Participants must be willing to consume provided snacks. Participants will also be excluded if they have history of gestational diabetes (GDM), diabetes, pre-eclampsia, hypertension, heart disease, hypothyroidism, or other metabolic abnormalities, current hyperemesis gravidarum, eating disorder, smoking, or are pregnant with multiples. Deviations from inclusion criteria will be at the discretion of the PI. Women that develop any of these medical conditions during pregnancy will be accounted for in the final analysis. This will be conducted at the University of Kansas Medical Center. We will recruit 56 pregnant women who are between 9-19 weeks in gestation. These women will be patients from the University of Kansas OBGYN clinic. The race/ethnic breakdown of participants will be 12.5% Hispanic, 30% Black, 40% White, 12.5% Asian and 5% classified as other. Following randomization and baseline testing, the intervention will begin and follow up measures will be acquired during pregnancy for outcome measures.
- (3) *Identify the sources of research material to be obtained from subjects.* In addition to data collected directly from participants infant birth characteristics (e.g., sex, gestational age at birth, birth weight, birth length, etc.) and health information up to 1 year of age and maternal delivery characteristics and 1 year pre- and post-partum health information will be extracted from the medical record. All participants will be assigned a nonidentifiable subject number. Data collected will be kept in [name] locked research laboratory. Only study personnel and [name] have keys to access this area. Electronic data will be kept

on a password protected computer in [name] laboratory on the shared drive. Only personnel approved by HSC and on the protocol will have access to the data.

(4) *Describe all potential risks.* No appreciable risk of physical, psychological, social, legal or other harm is expected. Blood will need to be drawn and may be associated with pain and the usual risks of blood letting. We are investigating between groups if differences are found for metabolic changes that occur during pregnancy. Many of the metabolic parameters we are exploring must be investigated in a fasted state or this would introduce error in the metabolic parameter (insulin, glucose, lipid panel, HbA1C, inflammatory markers). Measures will be collected at the CTSU Rainbow location and follow all safety protocols to ensure participant safety. In past protocols, we collect a fasting blood draw and took every precaution so that no harm comes to the mother or her baby. Women are instructed on the days leading up to their blood draw to drink plenty of water and to eat dinner and an evening snack if they are hungry the night before the blood draw. Appointments are scheduled first thing in the morning and we provide food and juice so that mothers eat immediately following the blood draw. We recorded no adverse events following this protocol. We have had no adverse events. All protocols are IRB approved and have undergone heavy scrutiny due to the special population we are working with. The DXA does emit radiation. In the moms, In the infants, three total body DXA scans will be completed over 12 months. The amount of radiation exposure for one DXA scan is equal to 0.001 mSV or the equivalent of exposure to 3 hours of natural background radiation. As a comparison, one chest x-ray is equal to 0.1 mSV or 10 days of exposure to natural background radiation. Over the course of 12 months, the total radiation exposure will be under a day of background radiation exposure. This is minimal especially considered it is spread over 12 months.

(5) *Describe the procedures for protecting against or minimizing any potential risks.* N/A. There are no known risks.

(6) *Discuss why the risks are reasonable in relation to anticipated benefits.* N/A. No known risks.

(7) *Plan for monitoring and reporting problems.* Adverse events will be assessed every 4 weeks during the dietary recalls during the 18-week intervention in the high-fiber group only. Baseline measurements will not be assessed for adverse events. Only adverse events related to gaining or losing too much weight or allergic reactions to the study food will be recorded. Research staff will immediately report any adverse events to the study PI for review. The study physician will review maternal and infant abnormal findings. If recommended by the study physician, abnormal findings will be communicated to the participant's physicians or infant's pediatrician.

(8) *Plan for handling study withdrawal/discontinuation.* Participants may discontinue study participation at any time in the study. Participants will be asked to sign a withdrawal consent. If participant does not sign a withdrawal consent, only data collected prior to withdrawal will be used.

Adequacy of Protection Against Risks

Describe plans for the recruitment of subjects and the consent procedures to be followed. Recruitment will be open to all pregnant women that meet the study inclusion criteria. The KUMC IRB will review and approve this study prior to implementation. Recruitment will only be performed under the supervision of the PI by trained research personnel who have completed human subjects and HIPAA training. Personnel will identify subjects who might be eligible by screening their electronic medical record in O2. Only medical information related to inclusion/exclusion criteria will be looked at. If determined eligible, research personnel will visit the patient at their scheduled clinic visit. OBGYN clinic staff will introduce study to potential subjects. Research personnel will discuss the study in detail and determine final eligibility. Participants missed at their OBGYN visit will be contacted via phone. If participants are interested, they will be followed up with via phone or email to determine enrollment and complete the informed consent. Informed consent will be obtained via phone or in person at the first study visit.

The women will be informed that the purpose of the study is to determine if a high fiber diet can help them gain the right amount of weight during pregnancy and that they will be placed in an intervention or control group. They will be told that if they participate in the study, regardless of their group assignment, that they will need to be seen two times during their pregnancy and four times after pregnancy. Further, they will be told if they are randomized to the intervention group they will be required to attend weekly video calls and report goals weekly to the study coordinator for 18 weeks.

Consent forms and HIPPA disclosure information per IRBs will be given to all subjects and their signatures witnessed. The consent forms will include a description of the study, nature of the data collection, the potential benefits and adverse reactions anticipated. Women will be assigned to group by random assignment provided by study statistician. The subjects will be told that their usual care would not be changed, withdrawn, or reduced if they chose to withdraw from the study at any time. The research team personnel will abide by all tenets of the University confidentiality policies, as well as the Privacy Protection for Research Subjects. All research staff will remain current in their NIH required Human Subjects protection and HIPAA certification.

Case Report Forms on all women will include medical information pertinent to the study (e.g., smoking history, blood pressure, pregnancy history, age, race, etc.) in addition to the information directly related to the study (e.g., height, pre-pregnancy and clinic weights, blood pressure, EDD by ultrasound or LMP, etc.). To maintain patient privacy, all case report forms, study reports and communications will identify the patient by the assigned patient number only. The medical record and originals of outcome data will be the source documents for the study. Any changes to the case report forms necessitated because they are odds with source documents will be initialed and dated by the Study Coordinators; and all Case Report Forms will be reviewed and approved by signature of the PI. Data monitors and auditors from the IRBs, and regulatory authorities will have access to the patient's original medical records for verification of data gathered on the case report forms and to audit the data collection process. Subjects will be made aware of persons who may see their protected health information in the informed consent document and may choose not to enroll in the study based on the information provided them in accord with 2003 HIPAA regulations. The patient's confidentiality will be maintained and will not be made publicly available to the extent permitted by the applicable laws and regulations.

Data monitors and auditors from the IRBs, and regulatory authorities will have access to the patient's original medical records for verification of data gathered on the case report forms and to audit the data collection process. Subjects will be made aware of persons who may see their protected health information in the informed consent document and may choose not to enroll in the study based on the information provided them in accord with 2003 HIPAA regulations. The patient's confidentiality will be maintained and will not be made publicly available to the extent permitted by the applicable laws and regulations.

The investigators will conduct the study in compliance with the protocol given approval by the KUMC IRB. Any changes to the protocol will require written approval from these committees prior to implementation, except when the modification is needed to eliminate an immediate hazard(s) to patients or if the change(s) involves only logistical or administrative aspects of the trial. Any departures from the protocol will be fully documented in the case report form and source documentation. IRB review occurs each year and newly dated consent forms are issued. The Research Assistant will keep the study binder that includes all communication with the IRB and CVs for all study personnel, and study personnel approved roles. The ultimate responsibility for ensuring that the study binders are in order will fall to the PI ([name]).

Patient recruitment and informed consent. All recruitment, consent and data forms for the study proposal will be submitted to the KUMC IRB prior to enrollment using templates and educational materials formatted as previously IRB-approved in the pilot study. Informed consent will be obtained by trained research personnel who have completed the NIH-approved Human Subjects' protection certification. Consent includes the standard elements: a study description, the potential risks, benefits and options for non-participation. All participants will be informed that they are free to withdraw from the study without changes in their usual care. Consent will be documented as a signed form and will be kept in a locked file at the study office. The study will be conducted in accordance with ethical principles founded in the Declaration of Helsinki. The IRB will review all appropriate study documentation to safeguard the rights, safety and well-being of the subjects. The protocol, informed consent, written information given to the subjects, safety updates, annual progress reports, and any revisions to these documents will be provided to the IRBs by the investigator. The method of obtaining and documenting the informed consent and the contents of the consent will comply with GCP and all applicable regulatory requirement(s).

Study personnel will identify subjects who might be eligible under a waiver issued by the IRB to look only at medical information related to inclusion/exclusion criteria for the study. No personal health information will be recorded until consent for the study is obtained in writing.

Protection against risk. Although no appreciable risk of physical or mental harm is expected to result from the protocol, procedures for dealing with adverse effects are established. Subjects will be instructed to report immediately to the study coordinator if any health problem occurs and to call the PI ([name]) at any time if they have questions or concerns. In such an event, it is the PI responsibility to answer those concerns honestly and to reiterate to the subject that they should continue in the trial only if they feel entirely comfortable with it. Subjects who choose to withdraw from the study will be reassured if they indicate the desire to withdraw.

Subjects will be protected against the risk of breaking confidentiality by decoupling of names from databases. Each participant will be assigned a numerical study ID and informed consent forms that include the subject's signature will be stored separately in locked file cabinets. For ensuring confidentiality, these are generally acknowledged to be the best methods known for ensuring that names are not associated with data. Only selected research staff will have access to the subjects' data. Subjects' informed consent includes the HIPAA compliance documentation approved by the KUMC IRB. Research team personnel will abide by all tenets of the University confidentiality policies as well as the Privacy Protection for Research Subjects.

Potential Benefits of Proposed Research

Describe all potential benefits. There are no direct benefits for participation in the study outside of contributing to the knowledge and formulation towards interventions that are successful at helping women to achieve appropriate GWG. This study could contribute to ways to improve maternal and infant health outcomes of pregnant women by improving GWG by identifying novel methods that can be used to encourage appropriate GWG.

Importance of Knowledge to be Gained

